10.0 Vulnerable Populations*

In order to ensure that this study is not biased against patients with the most severe infections, who are most likely to benefit from this imaging device, patients who are cognitively impaired (most likely due to head trauma) will be eligible for this study.

A legally authorized representative (LAR) with reasonable knowledge of the potential participant will be approached to consent on the patient's behalf if the patient cannot adequately answer at least 2 questions about the study or it is determined that the patient's level of cognition is not likely to change before study medication (ICG) can be administered. These questions will be to assess the participant's understanding of the study and what it means to participate, their appreciation of the consequences of participation, and their ability to consider alternatives to participation.

The choice of LAR will follow standard procedures. The following with be approached in this order of priority:

- Legal guardian
- Proxy (health care agent) named in an advance directive or durable power of attorney for health care;
- Family member or other surrogate identified by the state law on health care decisions.

Guidance will be provided to assist the LAR in making the consent decision. They will advised to base the decision on the participant's expressed wishes, or, if these are not known, what they believe the participant would have desired under the circumstances of the injury, their beliefs and values. If the LAR does not know what the participant would have wanted, the LAR will advised to base the decision with the participant's best interest in mind. They will be asked to carefully consider how much leeway the participant would likely give the LAR in making the choice about participation in the study.

This is in compliance with Checklist HRP-417 (Cognitively Impaired Adults). **11.0 Local Number of Subjects**

This is a pilot study to investigate the feasibility of obtaining fluorescence imaging following injection of ICG 24 hours prior to surgery for infection. This study seeks to enroll 20 patients. Several studies by this investigator inject ICG during surgery, however none have investigated ICG injection prior to surgery. The data collected in this pilot study will inform future studies involving ICG injection and the optimal time of injection.

12.0 Recruitment Methods

Participation in this research requires informed consent according to Institutional Review Board (IRB) guidelines and a signed IRB-approved Consent Form as the means of documenting this understanding.

Potential subjects will be identified either through the Orthopaedic outpatient clinic or by the patient's primary attending when the patient is currently an in-patient. Subjects who have undergone previous trauma surgeries and have developed an infection will be assessed for protocol inclusion criteria. This study requests a partial waiver of HIPAA for recruitment purposes. The partial waiver would allow for the surgeon to share with the research coordinator the patient name, sex, MRN number, age, underlying conditions as well as type and location of injury. There is an adequate plan to protect identifiers from improper use and disclosure as

information will only be used by study team members to determine whether a patient may be eligible. Information will only be communicated and stored using D-HH approved secure platforms. Information is only being used to determine if a patient is eligible for the study, for recruitment purposes. Once approached, if a patient is not interested, information will be destroyed. Protected health information will not be re-used or disclosed for another purpose. It will only be used for recruitment. This research could not practically be done without a partial waiver of HIPAA. This information is needed for recruitment. Patients will sign a full HIPAA Authorization when consenting to the study.

Subjects will be invited to participate in this study by a member of the orthopaedic care team, which will occur either at the time of consultation with the surgeon about the candidate's standard-of-care procedures or at another time agreed to by the potential participant, the candidate's surgeon or their designee. No advertisements or other promotional material will be used. No finder fees or recruitment incentives will be offered. Women of child bearing potential are eligible for enrollment into this study because ICG administration is not considered to present any additional risk for these women. The study will exclude women who are pregnant or breast-feeding as indicated in the exclusion criteria. Women of child-bearing potential, if asked to participate, will be given a pregnancy test as part of their standard of care testing prior to surgery and before administration of ICG.

All follow-up visits are within standard practice for these injuries/diagnoses.

Several additional strategies may be used to maximize follow-up including: 1) at the time of enrollment each participant will provide their own telephone number, as well as the name and address of a primary care physician, and the names and phone numbers of three people at different addresses with home the participant does not live and who are likely to be aware of the patient's whereabouts; 2) participants will receive a reminder card upon discharge for their next follow-up visit by the clinical staff; 3) participants w h o opt to receive text message reminders, will be given text message reminders; 4) follow-up will coincide with normal surgical infection clinic visits; and 5) if a participant refuses or is unable to return for the follow-up assessment, study personnel will determine his/her status with regards to major study outcomes by telephone.

13.0 Withdrawal of Subjects*

Participants will be removed from the protocol if:

- Study imaging is not completed for any reason.
- The subject withdraws consent.
- The subject has an occurrence of a significant clinical event that precludes imaging.

• The subject becomes pregnant before injection of ICG

If a participant is withdrawn from the protocol, the PI will mark the data of this subject as "withdrawn" and will add a detailed explanation about the cause of withdrawal in the database.

Subjects who withdraw after intraoperative imaging will be informed that data already collected may not be removed from the study database. Subjects will be asked if they would be willing to allow the investigator to collect data from their routine medical care. If the patient agrees then the research coordinator will collect follow up data from the electronic medical record at each follow up visit pertaining to the injury. The data collected will then be used in the statistical analysis portion that only involves the intraoperative image data and infection status. Those who do not wish to allow the investigator collect data from their electronic medical record will be asked to submit this request in writing to the investigator or a member of the research team.

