Guidance will be provided to assist the LAR in making the consent decision. They will advised to base the decision on the participant's expressed wishes, or, if these are not known, what they believe the participant would have desired under the circumstances of the injury, their beliefs and values. If the LAR does not know what the participant would have wanted, the LAR will advised to base the decision with the participant's best interest in mind. They will be asked to carefully consider how much leeway the participant would likely give the LAR in making the choice about participation in the study.

Recognizing that consent is an ongoing process, the study team will encourage the participants to ask additional questions that may arise during the course of their participation in the study.

If the patient is inpatient at the time of ICG administration then no additional IV access will need to be obtained. If the patient is dosed with ICG in the CRU then a qualified member of the CRU staff will insert the IV and then remove it before the patient leaves the CRU.

Patients will be administered a single, ICG, 2.5-5mg/kg dose 24 hours prior to surgery by a qualified member of their care team. The patient will be prepared and transported to surgery as per routine at Dartmouth-Hitchcock. In the OR, patient positioning, preparation of the surgical field, and draping will follow standard practice, of fracture fixation or joint fusion or requiring open surgical debridement/saucerization for osteomyelitis.

ICG fluorescence images will be acquired prior to surgical debridement. Debridement will then proceed per standard of care. The wound will be irrigated with a minimum of 3 liters irrigation with normal saline. After irrigation and debridement is completed another ICG fluorescence image will be acquired.

Costs associated with the purchase and administration of ICG will be billed directly to the study. Neither the patient or their health insurance provider will be responsible for any costs associated with the imaging procedures or the ICG administrations. The patient and / or their insurance company will be billed for a pregnancy test as part of routine surgery precautions for women of childbearing potential.

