The need for repeat debridement or tissue cultures will be left up to the treating surgeon. If repeat debridement is needed, pre- and post-debridement quantitative ICG fluorescence images will be obtained at each procedure. In the situation where a debridement surgery is repeated on another date, the subject will undergo consent as outlined in the protocol for each additional surgery for which imaging will be obtained. If the skin wound is unable to be closed, it will be left open with a sterile dressing until delayed coverage in collaboration with plastic surgery.

ICG will be administered by a qualified member of the care team. During administration patients will either be under the care and observation of the inpatient care teams or closely monitored by a qualified member of the CRU for at least 30 minutes post ICG administration. Postoperatively, patients are transferred to the Post-Anesthesia Care Unit (PACU) where they are monitored continuously by nursing staff supervised by anesthesiologists. During this entire time vital signs (including temperature, pulse, respiratory rate and blood pressure) are collected as standard of care. All clinical data will be reviewed for adverse events for a period of 24 hours post-injection by members of the care team.

Day of Injection Procedures	Pre- Infusion	Up To 24 Hours Post Injection
Pulse	Х	Х
Blood Pressure	Х	Х
Temperature	Х	Х
Respiratory Rate	Х	Х
Adverse Events		Х

Upon admission and throughout the hospital course, patients will be treated with antibiotics per standard of care by the orthopaedic service or in collaboration with infectious disease recommendations. Management of study patients including clinical and radiographic assessments will not differ from standard of care.

Study participants will be followed for a period of 6 months following injection of 24h ICG. Final follow-up will be at 6 months to capture all infectious complications (Figure C.2)³⁵. If a participant does not return to clinic, follow-up may be conducted by telephone. SSI and unplanned fracture-related reoperations will be identified at the time of diagnosis/occurrence and/or during each participant clinical assessment and medical record review that will occur during their routine outpatient clinic visits. *Figure C.2 follow up assessments*

Assessment	Visit 1: Enrollment	Visit 2: 6 months
Eligibility Screening	•	
Informed Consent	•	
Collection of Demographic and Fracture/Infection Data	•	
Collection of Surgical Data	•	

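### Section 13 removes participants with incomplete imaging even if they have already received ICG, which conflicts with the 6-month follow-up and SAE collection that section 5 starts at injection

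*Protocol*

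**What the plan says.** Protocol section 13 (Withdrawal of Subjects) lists the grounds for removal from the protocol. Two concern imaging: "Study imaging is not completed for any reason" and "The subject has an occurrence of a significant clinical event that precludes imaging". Neither depends on whether ICG has been given. The only ground in the list that refers to the injection is pregnancy, which is limited to the time before it.

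For a withdrawn participant, the investigator marks the data as withdrawn and "will add a detailed explanation about the cause of withdrawal in the database". A further paragraph deals with collection after withdrawal. It begins: "Subjects who withdraw after intraoperative imaging will be informed that data already collected may not be removed". It then asks for permission to collect data from routine care, and says of their use: "The data collected will then be used in the statistical analysis portion that only involves the intraoperative image data and infection status". It does not mention SAEs.

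Section 5 (Procedures Involved) sets the timing. Participants receive a single ICG "dose 24 hours prior to surgery by a qualified member of their care team". Images are taken before and after debridement. On follow-up it says: "Study participants will be followed for a period of 6 months following injection of 24h ICG". The follow-up assessment table in the same section marks SAE collection at enrollment and at 6 months. For the acute period it says: "All clinical data will be reviewed for adverse events for a period of 24 hours post-injection by members of the care team".

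**The concern.** Exposure comes about a day before imaging. Surgery may be cancelled, the device may fail, a reaction may occur, or the second image may be missed. In each case a participant has received ICG but has incomplete imaging. Section 5 counts that person's follow-up from the injection, while section 13 removes the same person from the protocol.

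If staff apply section 13 as written, systematic SAE and outcome collection up to 6 months ends for some exposed participants. The loss need not be random, because a clinical event after injection that prevents imaging is itself a ground for removal. The set followed for safety would then be defined by completed imaging and not by having received ICG.

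The rule also touches the purpose given in section 11, which describes a pilot of the feasibility of imaging after a 24-hour injection. Imaging failures after dosing are feasibility results and belong in the denominator of dosed participants.

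**Working it through.** The protocol gives no figure to reproduce on this point. The check is a comparison of rules, followed by an illustration of size.

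**1. The rules side by side**

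| Question | Section 5 | Section 13 |
|---|---|---|
| What starts or ends follow-up? | Starts at ICG injection, lasts 6 months | Ends on removal; incomplete imaging is a ground |
| Does ICG exposure matter? | Yes, it is the starting point | Not for the imaging grounds; only the pregnancy ground refers to injection |
| Are SAEs collected at 6 months? | Yes, per the table | Not mentioned for removed participants |

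For a participant who is dosed but not fully imaged, the two columns give different instructions. Because images are planned both before and after debridement, even someone with a usable first image and no second one arguably falls under the removal rule.

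**2. Random loss**

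Inputs: 20 participants (sections 1 and 11). Assumption: 1 or 2 dosed participants are unimaged, since the protocol gives no failure rate. With zero SAEs among n followed, the exact two-sided 95% upper limit is 1 − 0.025^(1/n):

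- n = 20: 16.8%
- n = 19: 17.6%
- n = 18: 18.5%

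**3. Loss related to the outcome**

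Assumption: one participant is removed and has the only later SAE.

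- All dosed participants followed: 1/20 = 5%, exact 95% CI 0.1% to 24.9%
- Removed participant not followed: 0/19 = 0%, upper limit 17.6%

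**4. How often an ICG reaction might be the cause**

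Inputs: the reaction rates in section 14, 0.15% mild, 0.2% moderate and 0.05% severe. Assumptions: the rates apply to this study and do not overlap.

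- Any grade: 0.0015 + 0.0020 + 0.0005 = 0.0040. The chance of at least one in 20 is 1 − 0.996^20 = 7.7%.
- Severe: 1 − 0.9995^20 = 1.0%.

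These figures show how rarely a reaction would be the cause of removal. They do not measure how many later SAEs would be missed.

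**The case against.** The strongest reply is that there is no express contradiction. Every withdrawal section limits a follow-up schedule, and section 13 never says that SAE collection stops on removal. That is correct as far as it goes, so this is an unreconciled conflict and not an order to stop safety follow-up. But section 13 gives staff no instruction to continue either.

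The paragraph on collection after withdrawal can also be read more widely, since only its first sentence is limited to those who withdraw after imaging. Even on that reading, collection depends on permission, the stated use is confined to image data and infection status, and SAEs are not named.

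An event that prevents the first image will mostly fall within the 24-hour review. Section 14 adds at least 30 minutes of observation and monitoring during hospitalization, and the cause of withdrawal is recorded. All of this stands. The triggering event is unlikely to be lost, and imaging failures can already be counted from the database. The gap is confined to later SAEs and outcomes, some of which may still appear in the routine chart.

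Safety is not a stated objective, and a participant with no image cannot contribute to the image-based aims. This too stands, and it limits the importance of the point. It does not make the matter one for the SAP alone, because an SAP can define analysis sets but cannot recover data that were not collected.

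Finally, the zero- and one-event scenarios may be unrealistic. The Background (section 2.0) cites repeat surgery in approximately 30% of patients. If such reoperations counted as SAEs and fell within 6 months (neither is stated), the chance of none in 20 would be 0.7^20, about 0.08%. The scenarios are therefore illustrations of the mechanism and not forecasts.

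**Conclusion.** The concern holds, as a modest defect that is cheap to correct. The two imaging grounds in section 13 ignore ICG exposure, while section 5 counts follow-up from exposure and schedules SAE collection at 6 months. Applied literally, section 13 makes safety and outcome follow-up conditional on completed imaging.

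Random loss of one or two participants hardly matters: the upper limit rises by 0.8 or 1.7 percentage points (17.6 − 16.8 and 18.5 − 16.8). Loss related to the event matters more, since 1/20 could be reported as 0/19, but this needs an imaging failure and the only later SAE in the same person. The number unimaged and the placement of the SAE are assumptions. The conflict between the two sections depends on neither.

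**What to change.** Amend section 13 and reconcile it with section 5:

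- Record imaging not completed after injection as an imaging failure, with its reason.
- Exclude such a participant only from the analyses that need the missing image.
- Continue 6-month SAE and outcome collection for every participant who received ICG, unless consent is withdrawn.
- Keep removal from the protocol for participants who never received ICG.
- When reporting the feasibility described in section 11, count imaging failures among dosed participants.

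The cost is a few sentences, plus chart review or telephone contact for a few more participants. Sections 5 and 12 already plan both within routine visits. The reported imaging completion rate may be lower, because failures after dosing would stay in the denominator.

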14.0 Risks to Subjects*

The risks to subjects are minimal in relation to anticipated benefits and/or knowledge that might reasonably be expected from the results of this clinical trial.

Risk of ICG injection: ICG (Indocyanine Green) will be administered intravenously once, 24h preoperatively. ICG is FDA approved for human use in angiography for ophthalmology and cardiology applications and is given routinely to patients in these clinical settings. The risks are considered minimal and consist of nausea, vomiting, hives, increased heart rate in subjects with particular sensitivity to the dye. ICG does contain sodium iodide and patients with a history of allergy to iodides will be excluded. Anaphylactic or urticardial reactions are rare but have been reported in patients both with and without a history of allergy to iodides. Anaphylactic deaths have been reported following IGG administration during cardiac catheterization. Reported rates of mild, moderate and severe adverse reactions to ICG are 0.15%, 0.2% and 0.05%. Every effort will be made to minimize this risk as much as possible. It is the standard of care at this institution to obtain information related to allergies, sensitivities and past medical histories upon patient arrival. Patients will also be monitored throughout their hospitalization, as is the standard of care, by everyone involved in their medical care for evidence of new or previously unknown reactions or sensitivities. Additionally, at all times ICG fluorescence imaging assessments are taking place, research staff and both surgical and anesthesia staff will monitor patients closely for any adverse reaction to ICG. Qualified inpatient medical staff or CRU staff will monitor patients for at least 30

minutes after ICG fluorescence injection has been completed. In the event of an unexpected allergic reaction, Dartmouth-Hitchcock Medical Center and all affiliated groups within this institution have procedures in place for managing patients with unknown or unexpected allergic reactions. If such a reaction were to occur, all standard of care treatments will be provided including but not limited to treatment with appropriate agents such as epinephrine, antihistamines and corticosteroids. Risk of infection from IV injection is also extremely rare but can occur. Pregnant women are excluded from the study. A pregnancy test is administered to women of child-bearing age on request at no cost.

Risk of infection from IV injection is extremely rare but can occur.

Prolonged operating room time: Because the ICG fluorescence assessments will take place in the operating room, participation in this study may increase the amount of time spent under surgical anesthesia in the operating room. For the average case, an additional 10 minutes at most will be incurred. However, the research staff will make every effort to minimize this risk by performing the assessment test while other required operative procedures are being performed.

Risk of confidentiality breach: Subjects enrolled in research are always exposed to additional risks of a breach in confidentiality, for example, of some elements of their personal health information that is made available to study investigators as part of their participation. The risk is 100%, but the occurrence rate of an actual breach is < 1% (to date, we are not aware of any subject participating in our studies who has experienced a detrimental breach of confidentiality or confidential information). Information about study subjects will be kept confidential and managed according to the requirements of the Health Insurance Portability and Accountability Act of 1996 (HIPAA). Risk of breach of confidentiality of the medical records and status of participants will be minimized. Databases which are used to store subject-sensitive information are password-protected and encrypted during file/data transfers from viewing terminals. Access will be limited to research team members who have undergone CPHS training at Dartmouth. Whenever possible and practical standard-of-care clinical data used in the research will be de-identified when under analysis.

